1 SUMMARY

Full title	Donor derived cell-free DNA and rejection of kidney allografts
Coordinating Investigator	Pr [name]
Scientific Director (if applicable)	[name]
Sponsor	Organ X Foundation
Scientific justification	
Allograft rejection is a major problem worldwide and results in the loss of thousands of transplants every year, with devastating consequences for patients in terms of mortality, morbidity and quality of life. With a prevalence of approximately 20% in the first-year after kidney transplantation, allograft rejection also represents a considerable economic burden for health care systems with the associated downstream cost related to graft failure and return to dialysis. The standard strategy to monitor rejection is based on surveillance of nonspecific functional markers such as serum creatinine level, estimated glomerular filtration rate, proteinuria and circulating donor-specific anti-HLA antibodies (DSA), which lack sensitivity and specificity. The current gold standard for diagnosing allograft rejection is the biopsy which is a potentially harmful, costly and often unnecessary procedure.
 
Recently, one promising non-invasive biomarkers has emerged in various fields such as oncology or gynecology for the monitoring of the patients: the cell-free DNA. In transplantation, donor-derived cell-free DNA (dd-cfDNA) detected in the blood of transplant recipients has been proposed as a noninvasive biomarker for the detection of rejection. However, dd-cfDNA has not been assessed in an unselected and deeply phenotyped population, with the comparison to the conventional parameters including functional, clinical or immunological factors to monitor patients and detect rejection.

Main objective and primary endpoint	
Main objectives
 
To assess the association of dd-cfDNA with the presence, activity and severity of allograft rejection, and determine whether dd-cfDNA adds value to standard of care monitoring parameters in detecting kidney allograft rejection

	
Primary endpoint Kidney allograft rejection (all causes) Time Frame: Up to 10 years after kidney transplantation

Design of the study	
Type of study: Multicenter international study Time Perspective: prospective

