Population of study participants	
Derivation cohort: Prospective cohort of kidney transplant recipients recruited in 2 French centers
 
Validation cohort: kidney transplant recipients in 11 North-American centers and 1 Belgian center with clinical, biological, histological and immunological data, and dd-cfDNA assessment.

Inclusion criteria	
 Recipients transplanted from a deceased or living donor, who undergone a kidney allograft biopsy with clinical, biological, histological and immunological data. Written informed consent at the time of transplantation for the center database.
Exclusion criteria	
 Combined organ transplantation Pregnant women Bone marrow transplant
Interventions or product under investigation	
This study involves minimal risk and constraints. The intervention consists in the evaluation of the risk of allograft rejection based on parameters measured as part of the standard of care and dd-cfDNA. No medicinal product is under investigation in this protocol.

Other interventions added by the study	
Gene expression measurement in allograft biopsies

Expected benefits for the participants and for society	
There will be no immediate individual benefit for the patient to participate in the study.
 
This study will be the first that evaluates the independent association of dd-cfDNA with rejection and its added value in addition to conventional features to predict kidney allograft rejection.
 
This first integrative system will improve the patient monitoring and will help physicians in decision-making process.

Minimal risks and constraints added by the study	
The intervention added by the study represents minimal risk and constraints for the patient as it will be embedded within the standard of care.
 
No additional puncture is performed; only one additional blood tube is taken for the measurement of dd-cfDNA.

Scope of the study	Kidney transplantation; non-invasive diagnosis of rejection for improving patient monitoring
Anticipated number of participants	
Number of participants with post-transplant risk evaluation:
 
Derivation prospective cohort: 1000 patients
 
External validation cohort: 1500 patients

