
Statistical analysis
	
Continuous variables will be described using means and standard deviations (SDs) or median and the interquartile range. We will compare means and proportions between groups using Student's t-test, analysis of variance (ANOVA) (Mann-Whitney test for donor specific antibodies (DSA) mean fluorescent intensity) or the chi-square test (or Fisher's exact test if appropriate).
 
We will evaluate the association between the dd-cfDNA levels and each allograft diagnosis (ABMR, TCMR, Mixed rejection, glomerulitis without rejection, polyomavirus nephritis, fibrosis, borderline changes, no specific lesions). Then, to investigate the association of dd-cfDNA with rejection severity, we will compare the mean dd-cfDNA level according to each active and chronic Banff lesion score (ranked from 0 to 3).
 
Evaluation of the association between dd-cfDNA and rejection
 
The associations between allograft rejection and clinical, functional, and immunologic factors will be first computed using logistic regression analyses. The factors identified in these analyses will be thereafter included in a final multivariable analysis if the p-value of the Wald test is < 0.1. Multivariable logistic regression analysis will be performed using a stepwise backward elimination until each predictor is associated with allograft rejection with a p-value below 0.05. The internal validity of the final model will be confirmed using a bootstrap procedure, which involves generating 1,000 datasets derived from resampling the original dataset and permitting the estimation of the biased corrected 95% CI and the accelerated bootstrap OR.
 
Assessment of the added value of dd-cfDNA
 
To evaluate the added value of dd-cfDNA, we will assess the performances of the reference model (including independent standard of care predictors of the final multivariable model) with and without dd-cfDNA to evaluate to risk of rejection. The performances of the models to predict rejection will be evaluated with the use of the accuracy of the model, which will be assessed based on its discrimination ability and calibration performance. For each model, the discrimination ability (i.e., the ability to separate patients with different prognoses) of the final model will be evaluated using Area under the curve (AUC). Calibration (the ability to provide unbiased rejection predictions in groups of similar patients) will be assessed based on a visual examination of the calibration plots.

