
	
We will follow the TRIPOD (Transparent Reporting of a Multivariable Prediction Model for Individual Prognosis or Diagnosis) statement for reporting multivariable prediction model development and validation.
 
Sensitivity analyses: We will investigate the independent association of dd-cfDNA with rejection and its added value in predicting rejection in different clinical scenarios (biopsies performed during the first year or after one-year post-transplantation, according to the subtypes of rejection, protocol biopsies or biopsies performed for clinical indication) and according to the patient ethnicity.
 
We will use R (version 4.1.2, R Foundation for Statistical Computing) and STATA (v17) for the descriptive and prediction analyses. Values of $p < 0.05$ will be considered significant, and all tests will be 2-tailed.

Sources of monetary support	The study is funded by the OrganX Foundation

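### Added value of dd-cfDNA is to be read from two AUCs with no confidence interval for their paired difference, and the intended external validation step is not written out

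*Combined protocol and SAP*

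**What the plan says.** All the available text is section 1 SUMMARY. The main objective has two parts: the association of dd-cfDNA with rejection, and to "determine whether dd-cfDNA adds value to standard of care monitoring parameters in detecting kidney allograft rejection".

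The Statistical analysis row, under Assessment of the added value of dd-cfDNA, compares the reference model "with and without dd-cfDNA to evaluate to risk of rejection". Discrimination "of the final model will be evaluated using Area under the curve (AUC", model by model. Calibration "will be assessed based on a visual examination of the calibration plots".

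The only interval named is in the preceding block on association. There, 1,000 bootstrap resamples support internal validity, "permitting the estimation of the biased corrected 95% CI and the accelerated bootstrap OR".

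The sensitivity analyses repeat the exercise, examining the marker's independent association and "its added value in predicting rejection in different clinical scenarios" (time since transplantation, rejection subtype, protocol or indication biopsy), and also by ethnicity.

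The population and sites rows define an external validation cohort of 1,500 patients at 12 sites, with "clinical, biological, histological and immunological data, and dd-cfDNA assessment". In the statistical text, validation beyond the bootstrap appears only through TRIPOD, cited as a "statement for reporting multivariable prediction model development and validation".

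**The concern.** The AUC gain can be had by subtraction, but its precision cannot. Both models are scored on the same patients, so the two AUC estimates are correlated, and the standard error of their difference needs that covariance. Two separate AUCs do not supply it, even if each has its own interval. A reader could not tell a small but real gain from a negligible one, least of all within the sensitivity subgroups.

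The second gap concerns transport beyond the two French centres. The text does not say whether coefficients are kept or refitted in the external cohort, nor which performance measures come from it. Left unwritten, these choices could be made after results are seen.

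A lesser point is that the reference model follows screening at p<0.1 and backward elimination to p<0.05, while the bootstrap's named outputs are odds ratios. Taken literally, the derivation AUCs would be apparent values. Correction is neither stated nor excluded.

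**Working it through.** The plan gives no expected AUC, gain or precision target, so there is no figure to reproduce. From the documents come the cohort sizes (1,000 and 1,500) and a first-year rejection prevalence of about 20%. Everything else is assumed.

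**1. Two AUCs do not determine the precision of the gain.** For n = 1,500 at 20% rejection there are 300 cases and 1,200 non-cases. The Hanley-McNeil variance is [A(1−A) + (n₁−1)(Q₁−A²) + (n₀−1)(Q₂−A²)]/(n₁n₀), with Q₁ = A/(2−A) and Q₂ = 2A²/(1+A).

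- A = 0.80: (0.16 + 299×0.0267 + 1199×0.0711)/360,000 = 0.000259, so SE = 0.0161.
- The 95% half-widths are 0.0316 for A = 0.80 and 0.0304 for A = 0.82.
- The paired SE is √(s₁² + s₂² − 2r·s₁s₂). For a gain of 0.02, the half-width is 0.031, 0.024 or 0.014 at r = 0.5, 0.7 or 0.9.

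The same two AUCs therefore give an interval that includes zero at r = 0.5 and 0.7 (0.02 ± 0.031 runs from −0.011 to 0.051) and one that excludes it at r = 0.9 (0.006 to 0.034). The planned outputs do not report r.

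**2. What the external cohort could deliver.** This was simulated with n = 1,500, 1,500 replicates, coefficients locked at their true values, one biopsy per patient, baseline AUC about 0.76 to 0.81, and a marker independent of the standard predictors. Half-width is 1.96 × empirical SE of the paired difference.

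| Rejection | Gain in AUC | 95% half-width | Gain with about 80% power |
|---|---|---|---|
| 10% | 0.007–0.075 | 0.009–0.028 | 0.024 |
| 20% | 0.007–0.079 | 0.007–0.022 | 0.015 |
| 40% | 0.008–0.082 | 0.006–0.018 | 0.011 |

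At 20%, a gain of 0.0161 has SE 0.0055, so the half-width is 1.96 × 0.0055 = 0.0108. The mean DeLong SE matched the empirical SE to within 0.0005. In an assumed subgroup of 375 (a quarter of 1,500), a gain of 0.0155 has half-width 0.0229, an interval of about −0.007 to 0.038.

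**3. Where DeLong is unsafe.** If both nested models are fitted and evaluated in the same patients (simulated at 20% rejection), DeLong rejected almost never with a useless marker: 0.4% one-sided at n = 1,000, against a nominal 2.5%. For a gain of 0.007, coverage of the nominal 95% interval was about 91 to 92% at n = 1,000 and 88% at n = 375. The method suits locked coefficients in new data, not refitted nested models.

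**4. Optimism.** This was simulated with n = 1,000, four true predictors, the planned screening and elimination, and 10 to 40% rejection. Apparent AUCs exceeded those in new patients by 0.006 to 0.015 with 20 candidate predictors and by 0.010 to 0.027 with 40. In the difference, optimism was only −0.001 to 0.002.

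**The case against.** The strongest reply is that validation is plainly intended. The cohort carries that name, has the predictors and the marker measured, and TRIPOD is adopted. The AUC and calibration sentences name no cohort and can be read as covering both. That stands: a reader might infer that no external validation is planned, and the documents do not support this. What is missing is the written step.

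A reader might also infer that the plan cannot show whether dd-cfDNA adds anything. It can: the Wald test and the bootstrap interval for the odds ratio address that. They do not say how much discrimination improves, or how precisely the improvement is known.

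Nor do the figures support the inference that missing optimism correction would inflate the gain. It would flatter each AUC and hardly touch the difference.

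It is also fair to say that this is silence in a summary, and that a paired interval can be computed later from the same predictions. Both limit the harm. Yet the summary does give selection thresholds, the bootstrap count and software versions, so it is not generally short of detail. Plots alone are an acceptable way to show calibration, and asking for more is a preference.

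**Conclusion.** The point holds as a specification gap, not a wrong analysis, and should be closed before the data are analysed. As written, half of the main objective would be answered by a gain of unstated precision, and the use of the external cohort is left to inference. The planned cohort is informative if the paired interval is computed: half-widths of about 0.006 to 0.028 over rejection of 10 to 40% and the gains examined. Subgroups may not be; at 375 patients a gain of about 0.016 would not be separable from zero.

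All these magnitudes rest on assumptions: the rejection share among biopsied patients, one biopsy each, the baseline AUC, a marker independent of standard predictors, and the subgroup size. The two gaps themselves do not depend on them. Confidence is medium, because only the summary was available.

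**What to change.** Add to the statistical analysis section:

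- **External cohort.** Apply both derivation equations, with and without dd-cfDNA, coefficients locked, to the 1,500 patients. Report the paired AUC difference with a 95% CI, overall and in the scenarios of the sensitivity analyses. Use DeLong, or a patient-level bootstrap if a patient contributes more than one biopsy.
- **Derivation cohort.** Do not use standard DeLong for nested models fitted in the same patients. Use the planned 1,000-sample bootstrap, repeating the screening and backward elimination in each resample, to obtain optimism-corrected AUCs, and report the AUC difference from the same procedure.
- **Optional.** Give the calibration intercept and slope beside the plots. Which cohort's result is primary, and whether to add net benefit, are for the sponsor to decide.

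The cost is a few sentences and some extra code. No extra patients or variables are needed, since the validation cohort is described as already having the data. The downside is a little more analysis and slightly less favourable AUCs.

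### Calibration is one of the two accuracy criteria for the added value of dd-cfDNA, yet it gets no estimate, interval or between-model contrast, only plots judged by eye

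*Combined protocol and SAP*

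**What the plan says.** The Statistical analysis row of Section 1 compares the reference model "with and without dd-cfDNA to evaluate to risk of rejection". Performance is judged by accuracy, "which will be assessed based on its discrimination ability and calibration performance". Discrimination is measured by the AUC. Calibration is defined as "the ability to provide unbiased rejection predictions in groups of similar patients" and "will be assessed based on a visual examination of the calibration plots".

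Three other statements could bear on this:

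- **Bootstrap.** The 1,000 resamples are described as "permitting the estimation of the biased corrected 95% CI and the accelerated bootstrap OR". That concerns the odds ratios.
- **TRIPOD.** It is adopted as a "statement for reporting multivariable prediction model development and validation". No calibration measure is named under it.
- **Significance level.** Two-sided 0.05 is set, but there is no calibration statistic to apply it to.

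The cohort sizes are 1,000 for derivation (2 French centres) and "External validation cohort: 1500 patients" (North American and Belgian centres). The text does not say in which cohort the calibration plots will be drawn.

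**The concern.** Added value over standard monitoring is half of the main objective, and calibration is one of its two criteria. The plan's own definition of calibration is about absence of bias, which has a size and a sampling error. Inspection of a plot reports neither. Two plots side by side also give no estimate of how calibration changes when dd-cfDNA is added.

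The AUC cannot fill this gap. It depends only on the ranking of patients, so it does not change if every predicted logit is shifted or multiplied by a positive constant. Models built in two French centres and applied in North America and Belgium may meet a different case mix and biopsy practice, in which absolute risks could drift while the AUC holds. The Summary expects the tool to support physicians' decisions, so the absolute risk matters as well as the ranking.

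**Working it through.** The plan states no calibration target or precision, so there is no figure to reproduce. The steps below ask what the plots can show at the planned sizes and whether numeric measures would be precise enough to be useful.

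**Inputs.** From the documents: n = 1,000 and 1,500; rejection about 20%, a first-year background figure; two-sided 0.05. Assumed: rejection of 10-40% as a range, because the cohort consists of biopsied recipients over up to 10 years; AUC 0.75-0.85, or linear-predictor SD 0.7-1.5.

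**Step 1: derivation data.** An unpenalised logistic model with an intercept satisfies Σ(y − p) = 0, so mean predicted risk equals the observed rate. Regressing y on the model's own linear predictor gives slope 1. Both hold by construction. A plot on the fitting data can show non-linearity, but not overall bias or overfitting.

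**Step 2: noise in one plotted group.** Ten groups of 1,500/10 = 150 patients. The 95% half-width is 1.96·√(p(1−p)/150).

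- At p = 0.20: 1.96·√(0.16/150) = 6.4 percentage points.
- At p = 0.53 (top decile with 20% rejection, AUC 0.75): 8.0 points.
- A 0.2 logit shift moves a 20% risk from logit −1.386 to −1.186, which is 23.4%. That is 3.4 points, about half the group's own half-width.

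**Step 3: precision of numeric measures, n = 1,500, 20% rejection (300 events).**

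- Calibration-in-the-large, 1.96/√(n·mean[p(1−p)]): ±0.14 to 0.15 logits.
- Slope, from the logistic information matrix: ±0.12 to 0.16.
- Observed/expected ratio, exp(1.96·√(0.8/300)): within a factor of 1.11.

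Over 10-30% rejection these become ±0.12 to 0.19, ±0.11 to 0.20, and a factor of 1.08 to 1.16. At n = 1,000 over the same range the slope is ±0.14 to 0.24.

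**Step 4: simulation, n = 1,500, 20% rejection.** Ten equal groups with Wilson 95% intervals. SD of the linear predictor is 1.0, except that the last row uses AUC 0.80. At most one group off the diagonal stands in for a plot that looks acceptable.

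| True state | At most 1 group off | 2 or more off | Numeric 95% CI excludes its target |
|---|---|---|---|
| Perfect | 91-93% | 7-9% | about 5% |
| Slope 0.80 | 34-58% | 42-66% | 73-87% (slope) |
| Shift 0.2 logit | about 60% | about 40% | about 84% (in-the-large) |
| Observed/expected 1.2 | 15% | 85% | 98% (in-the-large) |

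The spread for slope 0.80 comes from how the score is set up: whether the SD belongs to the predicted or the true linear predictor, and whether mean risk is held fixed. A slope error that also moves mean risk a long way is much easier to see on a plot.

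**Step 5: range.** Over 10-40% rejection and SD 0.7-1.5, the slope-0.80 figures run from about 23% to 83% (at most one group off) and about 34% to 97% (slope CI excludes 1). For the 0.2 shift they run from about 38% to 85% and about 52% to 95%.

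**The case against.** The strongest reply is that plots do carry information. With an observed/expected ratio of 1.2, 85% of simulated plots had two or more groups off the diagonal. With slope 0.80, 42-66% did, against 7-9% for a perfect model. A reader might infer that the plan has no means of finding biased predictions. The documents do not support that: a plot can reveal gross bias and its direction. What remains is lower sensitivity to moderate error and no stated size or uncertainty.

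A reader might also infer that the plan asserts that dd-cfDNA improves accuracy, and that this would rest on the AUC alone. It asserts no such thing; it says only that performance will be evaluated, and it attaches no decision rule to the plots.

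The simulated contrast depends on ten groups, a proxy for a reader's eye, and an assumed rejection rate and spread of risk. That stands, and the figures are illustrative. At the unfavourable end the slope interval would exclude 1 in only about 34% of trials, so numeric measures do not guarantee detection. They would, however, show the imprecision as a wide interval.

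Finally, a rule that declares miscalibration whenever an interval excludes 0 or 1 would make the answer depend on sample size. In simulation, slope 0.80 was flagged in 83% of trials at n = 1,500 and 67% at n = 1,000. That objection is right, and no such rule is recommended. None of these replies supplies the missing estimate, interval or contrast.

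**Conclusion.** The point holds as a gap in the stated method. Calibration is a named criterion for the added value of dd-cfDNA, its only assessment is inspection of plots, and neither the odds-ratio bootstrap nor the TRIPOD commitment provides a measure. This follows from the text and needs no assumption.

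The size does rest on assumptions. In the central illustration, moderate miscalibration leaves an acceptable-looking plot in roughly one third to three fifths of trials, while the matching interval excludes its target in roughly three quarters to nine tenths. The contrast varies widely with rejection rate, spread of risk and set-up of the score. The 1,500-patient figures also presuppose that calibration is examined in the external cohort, which the plan does not state. The change is worth making before analysis; the gap does not invalidate the study.

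**What to change.** Keep the plots, drawn as smoothed calibration curves with a confidence band, and add one paragraph to the statistical analysis:

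- **Estimates.** For the models with and without dd-cfDNA, report calibration-in-the-large and calibration slope, each with a 95% CI, in patients not used for fitting. Use the external cohort, or optimism-corrected bootstrap estimates in the derivation cohort with the backward elimination repeated in each resample. State which cohort each plot and estimate refers to.
- **Between-model contrast.** Report, for example, the difference in Brier score with a bootstrap 95% CI. The Brier score mixes discrimination and calibration, so it should be read beside the two slopes and intercepts.
- **Conclusion.** Base the statement on calibration on these estimates and intervals, not on a significance rule.
- **Recalibration.** If intercept or slope is re-estimated on the evaluation patients, label the resulting risks as not independently validated.

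The cost is a paragraph of wording, two small regressions per model and a bootstrap, with no new data. The downside is a little more analysis, and a miscalibrated model can no longer be called acceptable by eye.

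### Do the analyses by biopsy timing, biopsy reason, ethnicity and rejection subtype need a named between-group estimate, an interval for the AUC gain and a stated subtype comparator?

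*Combined protocol and SAP*

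**What the plan says.** All of the text is in the Statistical analysis section of the Summary.

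- **Sensitivity analyses.** "We will investigate the independent association of dd-cfDNA with rejection and its added value in predicting rejection in different clinical scenarios". The scenarios are biopsy timing (first year or later), then "according to the subtypes of rejection, protocol biopsies or biopsies performed for clinical indication", "and according to the patient ethnicity". Ethnicity categories are not given.
- **Evaluation of the association between dd-cfDNA and rejection.** The multivariable model is reduced by "stepwise backward elimination until each predictor is associated with allograft rejection with a p-value below 0.05". Its internal validity is checked with 1,000 bootstrap datasets, "permitting the estimation of the biased corrected 95% CI and the accelerated bootstrap OR". This is the only interval that the plan names.
- **Assessment of the added value of dd-cfDNA.** Added value is the performance of the "reference model (including independent standard of care predictors of the final multivariable model) with and without dd-cfDNA". For each model the discrimination "of the final model will be evaluated using Area under the curve (AUC"). No AUC difference and no interval for one is mentioned.
- **Significance level.** P-values below 0.05 "will be considered significant, and all tests will be 2-tailed".
- **Diagnoses.** Eight categories are listed for the descriptive comparison of dd-cfDNA levels. Three are rejection (antibody-mediated, T-cell-mediated, mixed). None is named as the reference for a subtype model.

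**The concern.** Sensitivity analysis usually means repeating the main analysis under a changed assumption. Analyses by timing, biopsy reason and ethnicity ask something else: whether the marker works equally well in different patients. A reader may then compare p-values across subgroups, and significance in one part only is weak evidence of a difference.

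Three further points add to the worry. If variable selection were rerun in each subgroup, backward elimination could drop dd-cfDNA where it misses p<0.05. AUC gains without intervals are hard to compare, because the same odds ratio gives a smaller gain where the reference model already discriminates well. And the odds ratio for a rejection subtype depends on whether the comparator is biopsies without rejection or all other biopsies.

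At stake would be statements that dd-cfDNA is more useful in one clinical scenario, ethnic group or rejection subtype than in another.

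**Working it through.** The documents give no power, event count, AUC, effect size or subgroup size, so there is no figure to reproduce. The inputs taken from them are 1000 derivation and 1500 validation patients, two-sided 0.05, and about 20% rejection in the first year. That last figure is background and not a design input. Everything else below is assumed.

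**1. Significant in one part only.** Assume the same odds ratio per SD in both parts, 20% rejection, no covariates, and splits of 40/60, 30/70 and 25/75. Approximate SE of the log odds ratio: 1/√(n × 0.2 × 0.8). Power ≈ Φ(ln OR/SE − 1.96).

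For OR 1.5 (ln OR = 0.405) and a 25/75 split of 1000:
- n = 250: SE 0.158, z 2.56, power 0.727.
- n = 750: SE 0.091, z 4.44, power 0.994.
- Discordance: 0.727 × 0.006 + 0.994 × 0.273 ≈ 0.28.

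The same steps give about 0.20 for 30/70 and 0.12 for 40/60. At least one of three, treated as independent: 1 − (0.72 × 0.80 × 0.88) ≈ 0.49. Simulation gives 45%. Simulated values for at least one discordant split:

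| Setting | OR 1.5 | OR 2.0 | OR 2.7 |
|---|---|---|---|
| 20% rejection, n=1000 | 45% | 2% | 0% |
| 20% rejection, n=1500 | 20% | 0.2% | 0% |
| 10% rejection, n=1000 | 76% | 20% | 1% |
| 30% rejection, n=1000 | 30% | 0.3% | 0% |
| 20%, n=1000, adjusted for a reference score (correlation 0.4) | 68% | 10% | 0.2% |

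The problem is real for a modest marker and almost absent for a strong one. It also needs a reading rule that the plan does not state.

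**2. Is there always an odds ratio to compare?** Yes. Sensitivity analyses covers both the association and the added value. Added value compares the reference model with and without dd-cfDNA, so the second model contains dd-cfDNA whatever elimination does. Rerun selection is nowhere stated.

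**3. Can a difference be assessed from the planned type of output?** For subgroups made up of different patients:

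ln(ratio of ORs) = ln OR₁ − ln OR₂, with SE = √(SE₁² + SE₂²), each SE ≈ (ln upper − ln lower)/(2 × 1.96).

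With the parts of 250 and 750 above and an observed OR of 1.5 in each: SE = √(0.158² + 0.091²) = 0.183. The ratio is 1.0, with 95% CI exp(±1.96 × 0.183) = 0.70 to 1.43. If the planned interval is carried into each subgroup, the information is there; only a named summary is missing. Bias-corrected bootstrap intervals need not be symmetric, so this is approximate.

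**4. AUC gain.** At correlation 0.4 and OR 2.0, the gain is 0.055, 0.033 and 0.022 at reference AUCs of 0.69, 0.78 and 0.84. In 250 patients with about 50 events, the 95% half-widths are 0.057, 0.040 and 0.028. So subgroup gains can differ with no difference in odds ratio, and each is imprecise.

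A Hanley-McNeil calculation agrees. For AUCs of 0.75 and 0.80 in a stratum of 500 (100 events), the SEs are 0.0300 and 0.0279. With correlation r between the AUCs, SE of the gain = √(0.0300² + 0.0279² − 2r × 0.0300 × 0.0279). That is 0.029 at r = 0.5 and 0.013 at r = 0.9, giving half-widths of 0.057 and 0.026. For the difference in gain between two such strata, multiply by √2: 0.080 and 0.036.

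No AUC interval is named in the main added-value analysis either, so this gap does not originate in the subgroups.

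**5. Subtype comparator.** Assuming 8% antibody-mediated, 8% T-cell-mediated and 4% mixed rejection, each with dd-cfDNA raised by 1 SD, the antibody-mediated odds ratio is 2.7 against no rejection and 2.2 against all others. If other injuries are 10% of the cohort, sit in the no-rejection group and have dd-cfDNA raised by 0.5 or 1 SD, 2.7 falls to 2.5 or 2.2. At 20% of the cohort it falls to 2.3 or 1.9. The size changes with the comparator, but the association remains clear under each.

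**The case for a change.** The strongest case for a change is this. Added value is half of the main objective, and these analyses extend it to clinical scenarios and ethnicity. The commitment to TRIPOD concerns reporting and fixes neither an estimate nor a reference group. A few lines would settle the model, the intervals and the comparator before results are seen, need no new data, and remove an avoidable analyst choice. For a strong marker the discordance argument fades, but the AUC-gain and comparator points remain.

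Most of that is fair as a description of what is unwritten, and the label is loose. It does not show that anything written leads to a wrong result. The stated aim is to investigate the marker within each scenario, for which within-scenario estimates are the right target and no interaction is required. The AUC interval and the choice of non-rejection diagnoses are general to the plan, so wording confined to the subgroups would not close either.

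A formal interaction analysis would also gain little. In simulation with an identical odds ratio of 1.5, a lone dd-cfDNA product term gives false interactions in 11–14% when the reference-score slopes are 0.5 and 1.0 in the two parts. Adding a subgroup-by-score product brings this back to 4–6%. Power for OR 2.0 against 1.5 is then only 22–29% at n=1000 for subgroup shares of 25–40%. Whether to add that term, and whether to adjust for multiplicity, are matters on which statisticians can differ.

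**Conclusion.** No change to the plan follows. The omissions are genuine, but they are missing detail in exploratory analyses. Sensitivity in place of subgroup is a matter of terminology.

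An analyst would be expected to keep the final model's predictors, give the dd-cfDNA odds ratio with its interval in each subgroup, and look at the ratio of odds ratios before saying that subgroups differ. The bootstrap already planned can also supply an interval for the AUC gain, by computing both AUCs in each resample. The subtype reference would be named when the models are reported.

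The risk arises if subgroups are fitted separately and compared by p-value alone, which the plan does not propose. At 20% rejection, unadjusted, the chance of at least one misleading split is 45% (n=1000) or 20% (n=1500) at an odds ratio of 1.5, at most 2% at 2.0, and 0% at 2.7. It is higher with fewer rejections or after adjustment. These figures rest on assumed effect sizes, subgroup shares, correlation and a two-level ethnicity split. The conclusion rests on the text: no subgroup claim is announced, and the with-dd-cfDNA model gives an odds ratio in every subgroup.
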